If 3 or fewer of the first 5 participants in the ipilimumab 5 mg/kg cohort (Prostate Cohort B) experience a TRAE leading to discontinuation of both agents, an additional 10 participants will be enrolled to receive nivolumab 1 mg/kg Q3W and ipilimumab 5 mg/kg Q6W for 2 cycles, then nivolumab maintenance 480 mg Q4W until PD or intolerable toxicity (Prostate Cohort B). If 4 or more of the first 5 participants of the ipilimumab 5 mg/kg cohort (Prostate Cohort B) experience a TRAE leading to discontinuation of both agents, an additional 10 participants will be enrolled to receive nivolumab 1 mg/kg Q3W and ipilimumab 3 mg/kg Q6W for 2 cycles, then nivolumab maintenance 480 mg Q4W until PD or intolerable toxicity (Prostate Cohort A). Only TRAEs leading to treatment discontinuation of both agents occurring up until the 5th participant in each cohort completes Cycle 1 will be included—dose delays for adverse events not otherwise meeting criteria at that time will not be counted. The stopping rule was chosen as this

corresponds to a > 80% chance that the toxicity rate in the cohort is > 40%, assuming a beta (0.8, 1.2) prior.

If either prostate cohort demonstrates 8 or greater TRAEs requiring discontinuation of therapy at any time, enrollment will be suspended until an ad hoc safety review convenes and provides a recommendation, as described above.

Table 9: Toxicity Criteria Requiring Permanent Treatment Discontinuation of Both Nivolumab and Ipilimumab (Amendment 3+ Advanced Prostate Cohort Only)

Participants should be monitored for the occurrence of any of the following AEs that are considered by the Investigator to be possibly, probably, or definitely related to ipilimumab, nivolumab, or the immunotherapy combination.
 
Treatment with all study intervention should be monitored for the occurrence of any of the following TRAEs, and if any of these events occur, action should be taken as follows:

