50	10	5	(3.7, 19.9)
40	10	4	(3.2, 21.2)
30	10	3	(2.6, 23.2)
160	20	32	(14.2, 26.5)
125	20	25	(13.5, 27.4)
100	20	20	(12.9, 28.3)
75	20	15	(11.9, 29.6)
50	20	10	(10.4, 31.8)
40	20	8	(9.5, 33.2)
30	20	6	(8.3, 35.2)
160	30	48	(23.1, 37.1)
125	30	38	(22.6, 38.5)
100	30	30	(21.4, 39.0)
75	30	22	(19.6, 39.6)
50	30	15	(18.1, 42.6)
40	30	12	(16.9, 44.0)
30	30	9	(15.2, 46.0)

A total of approximately 20 advanced prostate cancer participants with CD8 low tumors will be treated with the combination of nivolumab and ipilimumab, in 1 of 2 dosing cohorts. The first 10 participants enrolled will be randomly allocated by the Sponsor into one of two cohorts (5 participants per cohort) to evaluate the safety of different dose levels of ipilimumab in combination with nivolumab. If the higher dose level (ipilimumab 5 mg/kg + nivolumab 1 mg/kg) is determined to be tolerable per [Section 6.6.1.4](#), an additional 10 participants will be enrolled at this higher dose level (Prostate Cohort B). If the safety profile of Prostate Cohort B is deemed unacceptable, an additional 10 participants will be enrolled at the lower dose level (Prostate Cohort A).

We hypothesize that higher doses of ipilimumab will demonstrate a larger proportion of participants who convert from CD8 low to CD8 high. There is no prior for the expected proportion of participants who will convert from CD8 low to CD8 high at the various dose levels of ipilimumab. With 15 participants enrolled in Prostate Cohort B, Table 12 provides 95% credible intervals for possible CD8 conversion rates in the cohort. For example, a 95% credible interval assuming 6/15 (40%) participants converting in the cohort would be (17.7%, 64.9%).

Table 12: Credible Intervals for CD8 Conversion

Subgroup Size	CD8 Conversion Rate	Expected Successes	95% Credible Interval
15	20	3	(4.7, 42.8)
15	40	6	(17.7, 64.9)
15	60	9	(35.1, 82.3)

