#### **4.4 Safety Monitoring for Advanced Prostate Cancer**

As the combination regimen with ipilimumab 5 mg/kg has not been extensively studied, in addition to adverse events being reviewed by the Sponsor on an ongoing basis and investigator meetings convening approximately every 2 weeks to discuss and review safety events, a safety pause is included after the 5th patient has initiated treatment with ipilimumab at the 5 mg/kg dose level.

Enrollment will pause until all participants have been followed for at least 6 weeks. The safety pause will apply to both cohorts to preserve random allocation; however, the safety assessment as follows will apply to the ipilimumab 5 mg/kg cohort specifically. The initial 5 participants enrolled in the ipilimumab 5 mg/kg cohort will be observed for the occurrence of treatment-related adverse events (TRAEs) necessitating discontinuation of both agents from the beginning of treatment through completion of the first cycle (ie, 6 weeks).

If 3 or fewer of the first 5 participants in the ipilimumab 5 mg/kg cohort experience a TRAE leading to discontinuation of both agents, enrollment for that specific cohort will continue as planned until a total of approximately 10 participants are enrolled. If 4 or more of the first 5 participants of the ipilimumab 5 mg/kg cohort experience a TRAE leading to discontinuation of both agents, enrollment into the cohort will be suspended, and an ad hoc safety review (conducted by Investigators and Sponsor representatives) will be performed to assess the available data and provide a recommendation, which may include, but is not limited to, modification or discontinuation of the cohort, and will be documented in the study records. Only TRAEs leading to treatment discontinuation of both agents occurring up until the 5th

participant in each cohort completes Cycle 1 will be included—dose delays for adverse events not otherwise meeting criteria at that time will not be counted. The stopping rule was chosen as this corresponds to a > 80% chance that the toxicity rate in the cohort is > 40%, assuming a beta (0.8, 1.2) prior.

Should the ipilimumab 5 mg/kg cohort demonstrate 6 or greater treatment-related adverse events requiring discontinuation of therapy at any time, enrollment will be suspended until an ad hoc safety review convenes and provides a recommendation, as described above.

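### The later prostate enrolment-suspension trigger is 8 TRAEs in the protocol and 6 in the SAP; both count events without a denominator, and neither states what the number represents

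*Protocol*

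**What the plan says.** Protocol 6.6.1.4 contains two numerical rules for the prostate combination cohorts.

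- **First-five rule.** "If 4 or more of the first 5 participants of the ipilimumab 5 mg/kg cohort (Prostate Cohort B) experience a TRAE" that leads to stopping both agents, the next 10 participants go to Cohort A. Otherwise they go to Cohort B. Only events up to the time the fifth participant completes Cycle 1 count. The stated basis is that the rule "corresponds to a > 80% chance that the toxicity rate in the cohort is > 40%, assuming a beta (0.8, 1.2) prior".
- **Later rule.** "If either prostate cohort demonstrates 8 or greater TRAEs requiring discontinuation of therapy at any time", then "enrollment will be suspended until an ad hoc safety review convenes and provides a recommendation, as described above". It covers both cohorts and has no time limit. It refers to stopping therapy, not to stopping both agents. No basis is given for the 8. The review it points back to is not described in 6.6.1.4; only SAP 4.4 says who conducts it.

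On size, Protocol 9.1 allocates the first 10 participants "into one of two cohorts (5 participants per cohort") and then adds 10 to one cohort. Its precision table is written for the case "With 15 participants enrolled in Prostate Cohort B".

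SAP 4.4 has the same first-five count and the same justification. Its later rule differs: it applies should the 5 mg/kg cohort "demonstrate 6 or greater treatment-related adverse events requiring discontinuation of therapy at any time", and that cohort is planned at about 10. Protocol 9.4 and SAP section 2 both give the SAP precedence. SAP section 6, which lists differences from the protocol, does not mention this one.

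**The concern.** After the first-five decision, the later rule is the only numerical trigger left for the prostate cohorts. It alone covers later toxicity in the first five and all toxicity in the 10 added participants. Cohort A has no first-five rule of its own. The trial has no independent monitoring committee (Protocol 1.1). The tabulated monitoring limits in Protocol 9.3.1 start at 20 participants and are stated for the metastatic arms. The protocol itself describes the 5 mg/kg combination as not extensively studied.

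Three things are unclear. First, two thresholds and two scopes are in force. Second, the count is of events, so it does not correspond to any toxicity rate. Third, a fixed count with no number treated means very different things at 7 participants and at 15. A team applying the rule during expansion could not tell which number binds or what evidence it stands for.

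**Working it through.** **Inputs.** Prior beta(0.8, 1.2), reference rate 40% and level 80% (Protocol 6.6.1.4). Five per cohort, then 10 more in one, so 5 + 10 = 15 (Protocol 9.1). Later triggers of 8 (Protocol 6.6.1.4) and 6 with about 10 participants (SAP 4.4). Throughout, each affected participant is assumed to have one qualifying TRAE.

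**Formula.** With x affected of n treated, Pr(rate > 0.40) = 1 − F(0.40), where F is the distribution function of beta(0.8 + x, 1.2 + n − x).

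**Reproducing the plan's own figure.** 4/5 gives 0.942 and 3/5 gives 0.776. Four of five is the smallest count above 80%, so the stated justification is correct.

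**Same scale at larger n** (illustrative; the documents do not state it for the later rule):

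| n treated | Smallest x above 80% | Posterior at that x | Posterior at x − 1 |
|---|---|---|---|
| 6 | 4 | 0.875 | 0.657 |
| 7 | 5 | 0.934 | 0.788 |
| 8 | 5 | 0.875 | 0.688 |
| 9 | 5 | 0.8005 | 0.585 |
| 10 | 6 | 0.878 | 0.714 |
| 11 | 6 | 0.812 | 0.622 |
| 12 | 7 | 0.882 | 0.736 |
| 13 | 7 | 0.824 | 0.654 |
| 14 | 8 | 0.886 | 0.756 |
| 15 | 8 | 0.834 | 0.681 |

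Eight is the smallest qualifying count only at 14 and 15, and six only at 10 and 11. These ranges contain the full cohort sizes in the protocol (15) and the SAP (10).

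**States Cohort B can reach with 8 not acting.** The first-five rule permits expansion at 3/5. If the next participants are also affected, the sequence is 4/6 = 0.875, 5/7 = 0.934, 6/8 = 0.966, 7/9 = 0.983. Then 7/10 = 0.962, 7/11 = 0.928, 7/12 = 0.882 and 7/13 = 0.824 are also below 8. The SAP's 6 acts at 6/8 and beyond, but not at 4/6, 5/7 (0.934) or 5/8 (0.875).

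**How often, under assumed true rates.** Given passage of the first-five rule, expansion to 15 and immediate follow-up, the chance of passing 80% at some n from 6 to 15 with 7 or fewer affected is 29% at a true rate of 40%, 53% at 50% and 76% at 60%.

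**What an 80% boundary would cost.** Under the same conditions, checking 80% after every participant from 6 to 15 suspends enrolment with probability 31% at a true rate of 40%, against 17% for a fixed 8. At a true rate of 30% the figures are 12% and 4%.

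**Effect of counting events.** If participants have more than one qualifying TRAE, 8 events come from fewer than 8 people; at two each, 8/2 = 4 people suffice. This brings the trigger forward. The same count of 8 can therefore describe quite different rates.

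**The case against.** The strongest reply is that the 80% criterion does not belong to the later rule. In 6.6.1.4 it is given as the reason for the first-five rule, before the later rule appears. The two rules also differ in window (Cycle 1 versus any time), event (both agents versus therapy) and action (choice of cohort versus suspension for review). That stands. A reader might infer that the section applies its 80% criterion to the later rule and then breaks it; the documents do not say so.

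Nor is the 80% level the only candidate. Protocol 9.3.1.1 uses the same prior and 40% rate with a 97.5% level, for the metastatic arms. At that level the smallest counts are 8 at n = 10–11, 9 at 12–13 and 10 at 14–15, so a fixed 8 would be equal or stricter from n = 10 onward. Whether 8 is loose or strict depends on a criterion the protocol does not state.

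A reader might also infer that counting events is what keeps the rule from acting. It is not: event counting hastens the trigger, and only the fixed threshold delays it. Nor should an extreme state such as 7/7 be used against Cohort B: with at most 3 of the first 5 affected in the Cycle 1 window, that window alone allows at most 5/7.

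Finally, 8 is not the only route to a pause. Protocol 6.6.1.4 provides ongoing sponsor review and investigator meetings about every 2 weeks, and Protocol 10.1.9 lets the sponsor stop at any time. These are real safeguards, but they carry no number and do not settle which threshold applies.

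**Conclusion.** The point holds as a contradiction and an incomplete specification. The protocol and SAP disagree on the threshold (8 versus 6), the cohorts covered (either versus 5 mg/kg only) and the planned cohort size behind it (15 versus about 10). Both count events, omit the number treated, and change the discontinuation wording from the first-five rule.

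That each number was set for a full cohort is an inference from the arithmetic (8/15 = 0.834, 6/10 = 0.878), not something either document states. If it is right, a fixed 8 read as participants stays inactive at reachable states with posterior probabilities of 0.93 to 0.98, and becomes calibrated only when enrolment is nearly or fully complete. This rests on one event per affected participant and on borrowing the first-five criterion. It does not show that the protocol violates a criterion it set for this rule, nor that the rule always acts late.

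**What to change.** Reconcile Protocol 6.6.1.4 and SAP 4.4 on the threshold, the cohorts covered, the planned cohort size, and whether the event is discontinuation of both agents or of therapy. List any intended difference in SAP section 6. Define the count as participants with at least one qualifying TRAE out of participants treated. State the posterior criterion the threshold represents, whether the section's 80% or another, and give its operating characteristics over the sizes at which it will be applied. The choice of criterion is the sponsor's; the table above only shows what one stated criterion implies. Describe the ad hoc review in the protocol, since the text refers back to it.

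The drafting cost is a short table and a few sentences in each document. The operational cost depends on the criterion. Applying 80% at every n would pause enrolment earlier and more often, including when the true rate is 40% or below (31% versus 17% at 40%; 12% versus 4% at 30%, under the assumptions given).

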The disinhibition of T cell function induced by combined checkpoint blockade can lead to a distinct constellation of inflammatory side effects, collectively termed immune-related adverse events (irAEs). Ipilimumab, when given in combination with PD(L)-1 therapy, can induce a subset of adverse events, predominantly gastrointestinal, cutaneous, and hepatic, which in some cases can be severe. As such, irAE treatment guidelines have been established and widely implemented, and in most cases are effective in controlling these events (see Appendix 8; Nivolumab IB, 2020; Nivolumab IB Addendum, 2020).

In order to further mitigate the frequency and severity of these irAEs, only two doses of ipilimumab will be administered, and the doses will be given less frequently, on a 6 week schedule.

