6.6.1 Dose Modifications with Nivolumab and Ipilimumab

The Investigator may attribute each AE to the combination of nivolumab and ipilimumab or to nivolumab alone. Study participants may not have any dose modifications of nivolumab or ipilimumab doses in this study. After administration of the first dose ipilimumab, the Investigator may determine (based on clinical symptoms) the number of future doses of ipilimumab the participant will receive, for a maximum of 4 doses (advanced metastatic cancer) or for a maximum of 2 doses (advanced prostate cancer). If the ipilimumab is stopped and/or course has been completed, a repeat dose of ipilimumab at a later date is not permitted. Participants who stop ipilimumab dosing early due to toxicities may start nivolumab maintenance. If toxicity does not resolve or the criteria for resuming study intervention are not met, the participant must be discontinued from nivolumab monotherapy or nivolumab and ipilimumab combination therapy. Appropriate documentation is required regarding the drug to which the Investigator is attributing the AE. If, in the opinion of the Investigator, the toxicity is related to the combination of 2 agents, then both drugs should be held.

Specific anticipated or potential toxicities associated with the administration of nivolumab with or without ipilimumab, as well as the measures taken intended to avoid or minimize such toxicity in this trial, are described in the following sections.

6.6.1.1 Dose Modifications and Toxicity Management for Adverse Events Associated with Nivolumab with or without Ipilimumab

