AEs associated with nivolumab with or without ipilimumab exposure may represent an immunologic etiology. These irAEs may occur shortly after the first dose or several months after the last dose of treatment and may affect more than one body system simultaneously. Therefore, early recognition and initiation of treatment is critical to reduce complications. Based on existing clinical study data, drug-related AEs have included pulmonary toxicity, renal toxicity (including acute renal failure), endocrine abnormalities, gastrointestinal toxicity, dermatologic toxicity (including rash), and hepatotoxicity. For nivolumab monotherapy and combination therapy, the majority of these AEs have been managed successfully with supportive care and, in more severe cases, a combination of dose delay, permanent discontinuation, and/or use of corticosteroids or HRT (endocrinopathies). For suspected irAEs, ensure adequate evaluation to confirm etiology or exclude other causes. Additional procedures or tests such as bronchoscopy, endoscopy, and skin biopsy may be included as part of the evaluation.

For Amendments 1 and 2, dose modification and toxicity management guidelines for irAEs associated with nivolumab with or without ipilimumab are provided in [Table 7](#). For Amendment 3+ (advanced prostate cohorts), requirements for the discontinuation of study treatment for irAEs associated with nivolumab with or without ipilimumab are provided in [Table 9](#).

Table 7: Dose Modification and Toxicity Management Guidelines for Adverse Events Associated with Nivolumab with or without Ipilimumab

Drug-Related Adverse Event (AE) per CTCAE V5	Severity	Action Taken	Clarifications, Exceptions, and Resume Criteria
Gastrointestinal			
Colitis or Diarrhea	Grade 2	Delay dose	Dosing may resume when AE resolves to baseline
	Grade 3	Nivolumab monotherapy: Delay dose	Dosing may resume when AE resolves to baseline
		When administered with ipilimumab: Permanently Discontinue Ipilimumab	Nivolumab monotherapy may be resumed when AE resolves to baseline. If Grade 3 diarrhea or colitis recurs while on nivolumab monotherapy, permanently discontinue
	Grade 4	Permanently discontinue	
Renal			
Serum Creatinine Increased	Grade 2 or 3	Delay dose	Dosing may resume when AE resolves to Grade \leq 1 or baseline value
	Grade 4	Permanently discontinue	
Pulmonary			
Pneumonitis	Grade 2	Delay dose	Dosing may resume after pneumonitis has resolved to \leq Grade 1.
	Grade 3 or 4	Permanently discontinue	

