
• Any Grade 2 drug-related uveitis, eye pain or blurred vision that does not respond to topical therapy and does not improve to Grade 1 severity within the re-treatment period OR requires systemic treatment.• Any Grade 3 non-skin, drug-related AE lasting > 7 days, or recurs with the following exceptions for laboratory abnormalities, diarrhea, colitis, neurologic toxicity, drug-related uveitis, pneumonitis, bronchospasm, hypersensitivity reactions, infusion reactions, and endocrinopathies:
○ Grade 3 drug-related diarrhea, colitis, neurologic toxicity, uveitis, pneumonitis, bronchospasm, myocarditis, hypersensitivity reaction, or infusion reaction of any duration requires discontinuation.○ Grade 3 drug-related endocrinopathies, adequately controlled with only physiologic hormone replacement do not require discontinuation. Adrenal insufficiency requires discontinuation regardless of control with hormone replacement.○ Grade 3 drug-related laboratory abnormalities do not require treatment discontinuation except:
▪ Grade 3 drug-related thrombocytopenia > 7 days or associated with bleeding requires discontinuation.▪ Any drug-related liver function test abnormality that meets the following criteria require discontinuation:
• Grade ≥ 3 drug-related AST, ALT or total bilirubin requires discontinuation.
○ In most cases of Grade 3 AST, ALT evaluation study drug(s) will be permanently discontinued. If the investigator determines a possible favorable benefit/risk ratio that warrants continuation of study drug(s), a discussion between the investigator and the Medical Monitor (or designee) must occur.• Concurrent AST or ALT > 3x ULN and total bilirubin > 2x ULN.• Any Grade 4 drug-related adverse event or laboratory abnormality (including but not limited to creatinine, AST, ALT, or total bilirubin), except for the following events which do not require discontinuation:
○ Grade 4 neutropenia ≤ 7 days.○ Grade 4 lymphopenia or leukopenia or asymptomatic amylase or lipase.○ Isolated Grade 4 electrolyte imbalances/abnormalities that are not associated with clinical sequelae and are corrected with supplementation/appropriate management within 72 hours of their onset.○ Grade 4 drug-related endocrinopathy adverse events, such as, hyper- or hypothyroidism, or glucose intolerance, which resolve or are adequately controlled with physiologic hormone replacement (corticosteroids, thyroid hormones) or glucose-controlling agents, respectively, may not require discontinuation after discussion with and approval from the Medical Monitor (or designee).• Any event that leads to delay in dosing lasting > 12 weeks from the previous dose requires discontinuation, with the following exceptions:
○ Dosing delays to allow for prolonged steroid tapers to manage drug-related adverse events are allowed.

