
- Dosing delays lasting > 6 weeks from the previous dose that occur for non-drug-related reasons may be allowed if approved by the Medical Monitor (or designee).
- Prior to re-initiating treatment in a participant with a dosing delay lasting > 6 weeks, the Medical Monitor (or designee) must be consulted. Tumor assessments should continue as per protocol even if dosing is delayed. Periodic study visits to assess safety and laboratory studies should also continue per SOA or more frequently if clinically indicated during such dosing delays.
- Any adverse event, laboratory abnormality, or intercurrent illness which, in the judgment of the Investigator, presents a substantial clinical risk to the participant with continued nivolumab dosing.

AE = adverse event; ALT = alanine aminotransferase; AST = aspartate aminotransferase; SOA = Schedule of Assessments; TRAEs = treatment-related adverse event; ULN = upper limit of normal

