Patients on IV steroids may be switched to an equivalent dose of oral corticosteroids (e.g. prednisone) at start of tapering or earlier, after sustained clinical improvement is observed. Lower bioavailability of oral corticosteroids should be taken into account when switching to the equivalent dose of oral corticosteroids.

*Refer to NCI CTCAE v5 for term-specific grading criteria.

**If Steven-Johnson Syndrome (SJS), toxic epidermal necrosis (TEN), Drug Reaction with Eosinophilia and Systemic Symptoms (DRESS) is suspected, withhold I-O therapy and refer patient for specialized care for assessment and treatment. If SJS, TEN, or DRESS is diagnosed, permanently discontinue I-O therapy.

Neurological Adverse Event Management Algorithm

Rule out non-inflammatory causes. If non-inflammatory cause, treat accordingly and continue I-O therapy.

[figure not shown]

Patients on IV steroids may be switched to an equivalent dose of oral corticosteroids (eg. prednisone) at start of tapering or earlier, after sustained clinical improvement is observed. Lower bioavailability of oral corticosteroids should be taken into account when switching to the equivalent dose of oral corticosteroids.

^aDiscontinue for any grade myasthenia gravis, Guillain-Barre syndrome, treatment-related myelitis, or encephalitis.

Pulmonary Adverse Event Management Algorithm

[figure not shown]
Rule out non-inflammatory causes. If non-inflammatory cause, treat accordingly and continue I-O therapy. Evaluate with imaging and pulmonary consultation.

Patients on IV steroids may be switched to an equivalent dose of oral corticosteroids (eg, prednisone) at start of tapering or earlier, after sustained clinical improvement is observed. Lower bioavailability of oral corticosteroids should be taken into account when switching to the equivalent dose of oral corticosteroids.

Renal Adverse Event Management Algorithm

[figure not shown]
Rule out non-inflammatory causes. If non-inflammatory cause, treat accordingly and continue I-O therapy.

Patients on IV steroids may be switched to an equivalent dose of oral corticosteroids (eg, prednisone) at start of tapering or earlier, after sustained clinical improvement is observed. Lower bioavailability of oral corticosteroids should be taken into account when switching to the equivalent dose of oral corticosteroids.

Myocarditis Adverse Event Management Algorithm

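### Table 9, the required-stop list for the prostate cohorts, omits seven diagnoses for which Appendix 8 says to discontinue at any grade

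*Protocol*

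**What the plan says.** Protocol section 6.6.1.1 assigns Table 7 to Amendments 1 and 2 and sends the prostate cohorts to Table 9: "For Amendment 3+ (advanced prostate cohorts), requirements for the discontinuation of study treatment for irAEs" are found there. Table 9's title says its criteria require permanent discontinuation of both agents.

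The lines of Table 9 that bear on this point are:

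- **Grade 3, named events:** "Grade 3 drug-related diarrhea, colitis, neurologic toxicity, uveitis, pneumonitis, bronchospasm, myocarditis, hypersensitivity reaction, or infusion reaction of any duration requires discontinuation".
- **Grade 3, general rule:** limited to non-skin events that last more than 7 days or recur.
- **Grade 4:** "Any Grade 4 drug-related adverse event or laboratory abnormality", with listed exceptions.
- **Grade 2:** the only event-specific stop is for eye events.
- **Any grade:** a dosing delay beyond 12 weeks (prolonged steroid tapers are exempt), combined liver criteria, and anything that "in the judgment of the Investigator, presents a substantial clinical risk to the participant with continued nivolumab dosing".

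Appendix 8 is stricter. Its neurological algorithm says to stop, whatever the grade, for Guillain-Barré syndrome, myasthenia gravis, encephalitis and treatment-related myelitis. Its skin algorithm says: "If SJS, TEN, or DRESS is diagnosed, permanently discontinue I-O therapy". Section 4.3.2.1, written for Prostate Cohorts A and B, relies on that appendix: "irAE treatment guidelines have been established and widely implemented, and in most cases are effective in controlling these events (see Appendix 8".

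**The concern.** The list that carries the word requirements is looser, for seven serious immune-related diagnoses, than the appendix meant to guide management. The protocol gives no reason.

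Elsewhere Table 9 is the stricter list. For Grade 3 diarrhea or colitis, Table 7 and Appendix 8 let nivolumab resume, while Table 9 stops both drugs. Table 9 also stops for Grade 3 adrenal insufficiency that hormone replacement controls, where Table 7 may not. The reversal for these seven diagnoses therefore looks unintended.

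An investigator who treats Table 9 as the controlling list could hold treatment and later restart it after an event for which the protocol elsewhere says to stop. The prostate cohorts include nivolumab 1 mg/kg with ipilimumab 5 mg/kg, above the 3 mg/kg that section 4.3.2.1 gives as the highest ipilimumab dose tested with that nivolumab dose. Section 6.6.1.4 also cites Table 9 as the list of events requiring discontinuation in the Cohort B safety assessment, so the list ought to be complete.

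**Working it through.** This is mainly a comparison of texts. The plan states no figure for it.

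**1. Which list binds.** Section 6.6.1.1 makes Table 9 the requirement for the prostate cohorts, with or without ipilimumab. Appendix 8 also applies to them: section 6.6 introduces it without a cohort limit, and section 4.3.2.1 cites it for Cohorts A and B. Section 6.6 describes the algorithms as an aid to investigators, which is weaker than a requirement.

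**2. Neurologic diagnoses in Table 9.** Grade 3 is a named stop and Grade 4 falls under the general Grade 4 line. No line names any of the four diagnoses at Grade 1 or 2. Table 7 makes all four (drug-related, for encephalitis and myelitis) permanent stops at any grade in the other arms.

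**3. Confirmed SJS, TEN or DRESS in Table 9.** Table 7 and Appendix 8 class these as skin events. The general Grade 3 rule leaves skin events out, so on severity alone only the Grade 4 line reaches them.

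**4. Coverage count, each diagnosis at Grades 1 to 4.**

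| Diagnoses | Combinations | Table 9 mandates a stop | Appendix 8 | Table 7 |
|---|---|---|---|---|
| Four neurologic | 4 × 4 = 16 | 4 × 2 = 8 | 16 | 16 |
| SJS, TEN, DRESS | 3 × 4 = 12 | 3 × 1 = 3 | 12 | no explicit row once confirmed |
| Total | 28 | 11 | 28 | not totalled |

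The gap is (16 − 8) + (12 − 3) = 8 + 9 = 17. It is an upper bound, since some diagnosis-grade pairs may not exist under CTCAE. If Table 9's Grade 3 hypersensitivity line were read to include DRESS, coverage would be 11 + 1 = 12 and the gap 28 − 12 = 16.

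**5. A worked case.** A prostate participant develops Grade 2 myasthenia gravis, attributed to the combination (the default in section 10.5.3).

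- Section 6.6.1: "If, in the opinion of the Investigator, the toxicity is related to the combination of 2 agents, then both drugs should be held".
- Table 9: no event-specific stop.
- Appendix 8: discontinue.
- Section 6.6.1, if the investigator stops ipilimumab alone: "Participants who stop ipilimumab dosing early due to toxicities may start nivolumab maintenance".

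The judgment line in Table 9 or section 7.1 may still lead to a stop, but neither names the diagnosis.

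**6. The Cohort B gate, for context.** Section 6.6.1.4 says that 4 or more of 5 corresponds to more than an 80% chance that the toxicity rate exceeds 40%, under a beta(0.8, 1.2) prior. The posterior after x events in 5 is beta(0.8 + x, 1.2 + 5 − x).

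- x = 3: beta(3.8, 3.2), Pr(rate > 0.40) = 0.776.
- x = 4: beta(4.8, 2.2), Pr(rate > 0.40) = 0.942.

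Four is the smallest count above 80%, so the plan's figure reproduces and is not in dispute.

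**The case against.** The strongest reply is that the two lists are compatible. Appendix 8 orders the stop, nothing says Table 9 is exhaustive, and no line in Table 9 permits continuing after these diagnoses. An investigator who follows both documents stops. Section 6.6.1 adds that a participant whose toxicity does not resolve, or who does not meet the criteria for resuming, must come off treatment. Section 7.1 requires stopping for any condition that may endanger the participant.

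Much of this stands: it is an inconsistency and not an absent rule. It does not close the gap, for these reasons:

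- Appendix 8 is guidance, whereas Table 9 is the requirement.
- The judgment routes are discretionary.
- The resume-criteria sentence does not bar a restart after a resolved Grade 2 event, because no resume criteria for these diagnoses are stated for the prostate cohorts.
- The 12-week delay rule exempts prolonged steroid tapers for drug-related events.

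Four narrower objections also have some force:

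- Table 7 has no explicit row for confirmed SJS, TEN or DRESS either. It delays on suspicion and allows a restart only once they are ruled out. The skin part is therefore not peculiar to Table 9.
- The clinician dashboard in section 8.8 uses Table 7, which has the any-grade neurologic stops. It is optional and advisory.
- The gate counts actual discontinuations of both agents, so a stop made under Appendix 8 or on judgment could still count.
- The untested-dose argument applies to Cohort B only.

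**Conclusion.** The concern holds. Table 9 has no event-specific stop for the four neurologic diagnoses at Grades 1-2, or for confirmed SJS, TEN or DRESS below Grade 4, while Appendix 8 says to discontinue for all seven. The gap is at most 17 of 28 diagnosis-grade combinations. This rests on reading DRESS as a skin event, as the protocol does, and on counting every grade as possible.

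The affected group is about 20 CD8-low prostate participants plus the CD8-high ones, including any who cross over; the documents do not give those numbers. Nothing is claimed about how often these events occur. The change should be made, because it aligns a binding safety list with the protocol's own guidance.

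**What to change.** Add one bullet to Table 9:

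> Drug-related myasthenia gravis, Guillain-Barré syndrome, myelitis or encephalitis at any grade, and confirmed drug-related SJS, TEN or DRESS at any grade: permanently discontinue both nivolumab and ipilimumab.

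Optionally, in section 6.6.1, add to the sentence that allows nivolumab maintenance after an early ipilimumab stop an exception for events listed in Table 9 (prostate cohorts). This only clarifies, since Table 9's title already requires stopping both agents.

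The cost is one line of text, with no added procedures, participants or analyses. The downside is losing the option to continue nivolumab after a mild case. Appendix 8 already rules that out for all seven diagnoses, and Table 7 rules it out for the four neurologic ones in the metastatic arms.
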